2. STATISTICAL HYPOTHESES

The primary efficacy endpoint of this study is the proportion of participants who achieved an ACR 20 response at Week 24 (refer to Section 5.3.4 for endpoint definition and analyses). This endpoint was chosen because it is well-accepted by regulatory authorities and the clinical PsA community.

The hypotheses related to the primary endpoint are that:

- 1. **(H1)** Treatment with guselkumab 100 mg SC q4w is superior to treatment with placebo SC with respect to reduction of PsA signs and symptoms as measured by proportion of participants who achieved an ACR 20 response at Week 24 (*primary hypothesis*); and
- 2. **(H2)** Treatment with guselkumab 100 mg SC at Week 0, Week 4 and then q8w is superior to treatment with placebo SC with respect to reduction of PsA signs and symptoms as measured by proportion of participants who achieved an ACR 20 response at Week 24 (key *secondary hypotheses*).

The first hypothesis (H1) is the **primary hypothesis** for this study. If the first hypothesis achieves the statistical significance at a 2-sided α -level of 0.05, the study will be considered positive.

In addition to the primary endpoint, there are 10 major secondary endpoints in this study (refer to Section 5.3.5 for endpoint definitions and analyses). The hypotheses related to the major secondary (all are major secondary hypotheses) are provided in Section 6.10 (Appendix 10).

For hypothesis testing order and multiplicity adjustment, refer to Section 5.3.3.2.

3. SAMPLE SIZE DETERMINATION

The planned enrollment in the study is approximately 450 participants. The sample size selection was determined based on the primary endpoint of proportion of participants who achieve an ACR 20 response at Week 24. The assumptions are based on the PSA3001 and PSA3003 studies.

3.1. Primary Endpoint – ACR 20 Response at Week 24

In the PSA3001 study, the ACR 20 response rates in the overall efficacy population at Week 24 were 22.2%, 52.0%, and 59.4%, for the placebo, guselkumab SC 100 mg q8w, and guselkumab 100 mg q4w treatment groups, respectively.

In the PSA3003 study which included participants who have an inadequate response or intolerance to up to 2 prior anti-TNFs, the ACR 20 response rates at Week 24 were 19.8% and 44.4%, for placebo and guselkumab SC 100 mg q8w, respectively.

For this study, assuming an ACR 20 response rate comparable to those in PSA3001 and PSA3003 in each of the guselkumab groups and the placebo group, a sample size of 150 participants per group for each of the guselkumab treatment groups and placebo will have >90% power to detect differences between each guselkumab treatment group and placebo for the primary endpoint assuming a 2-sided alpha level of 0.05 (Table 3). The sample size calculations assume that 100% of the effect observed in PSA3001 and PSA3003 will be observed. If only 70 or 80% of the effect seen in PSA3001 and PSA3003 is observed, the power will still exceed 90% for the Primary endpoint.

			Mean or proportion		Difference (Δ)	Power (n=150
Endpoint Source		e	Placebo Guselkumab Group Group			p=0.05)
Primary: ACR20 at	Week 24					
	PSA3001	Q8	22%	52%	30%	>99%
	PSA3001	Q4	22%	59%	37%	>99%
	PSA3003 ^a	Q8	19.8%	44.4%	24.6%	>99%
a: PSA3003 (COSMO	OS) data is for Q8	W only	•	•		

Table 3: Power Calculations for Primary Endpoint Based on 150 per Treatment Group

3.2. Major Secondary

Table 4 provides the statistical power for major secondary with 150 participants per treatment group. The study power ranges approximately from 44% to 99%.

Table 4: Power Calculations for Major Secondary Endpoint Based on 150 Participants per Treatment Group

			Mea	n or proportion			
Endpoint	Source		Placebo	Guselkumab Group	SDa	Difference (A)	Power (n=150 p=0.05)
(multiplicity controlled))						
IGA at Week 24	PSA3001	Q8	15%	57%		42%	>99%
	PSA3001	Q4	15%	75%		60%	>99%
PASI90	PSA3001	Q8	11.5%	50.0%		38.5%	>99%
	PSA3001	Q4	11.5%	62.9%		51.4%	>99%
	PSA3003 ^b	Q8	7.5%	51.1%		43.6%	>99%
HAQ-DI at Week 24	PSA3001	Q8	-0.07	-0.32	0.56	0.25	97%
	PSA3001	Q4	-0.07	-0.40	0.56	0.33	>99%
	PSA3003 ^b	Q8	-0.009	-0.178	0.52	0.169	>99%
SF-36 (PCS) at Week 24	PSA3001	Q8	1.96	6.10	7.72	4.14	>99%
	PSA3001	Q4	1.96	6.87	7.72	4.91	>99%
	PSA3003 ^b	Q8	-0.387	3.514	6.61	3.901	>99%
FACIT-F at Week 24	PSA3002	Q8	3.56	7.55	9.87	3.99	87%
	PSA3002	Q4	3.56	7.11	9.87	3.55	93%
	PSA3003 ^b	Q8	1.050	4.607	8.67	3.557	94%
MDA	PSA3001	Q8	11.1%	22.8%		11.7%	78%
	PSA3001	Q4	11.1%	30.5%		19.4%	99%
	PSA3003 ^b	Q8	3.1%	14.8%		11.7%	95%
Major secondary (weak	ly controlled	I)		•		1	
ACR20 at Week 16	PSA3001	Q8	25%	52%		27%	>99%
	PSA3001	Q4	25%	60%		35%	>99%
	PSA3003 ^b	Q8	16.7%	41.3%		24.6%	>99%

			Mea	n or proportion			
Endpoint	Source		Placebo	Guselkumab Group	SDa	Difference (Δ)	Power (n=150 p=0.05)
ACR50 at Week 24	PSA3001	Q8	9%	30%		21%	>99
	PSA3001	Q4	9%	36%		27%	>99%
	PSA3003 ^b	Q8	5.2%	19.6%		14.4%	97%
ACR50 at Week 16	PSA3001	Q8	13%	23%		10%	62%
	PSA3001	Q4	13%	27%		14%	87%
	PSA3003 ^b	Q8	5.2%	14.3%		9.1%	77%
ACR70 at Week 24	PSA3001	Q8	6%	12%		6%	44%
	PSA3001	Q4	6%	20%		14%	96%
	PSA3003 ^b	Q8	1.0%	7.9%		6.9%	84%

^a: Used the largest standard deviation among the treatment groups.

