1.2. Study Design

[figure not shown]
This is a Phase 3b, multicenter, randomized, double-blind, placebo-controlled interventional study in participants with active PsA who had an inadequate response and/or intolerance to one prior anti-TNF.

A target of 450 participants will be randomly assigned in this study with 150 participants planned per intervention group: guselkumab q8w (n=150), guselkumab q4w (n=150), or placebo (n=150).

Stable doses of concomitant non-steroidal anti-inflammatory drugs (NSAIDs), oral corticosteroids (≤10 mg/day prednisone equivalent) and selected non-biologic DMARDs (methotrexate [MTX], sulfasalazine [SSZ], hydroxychloroquine [HCQ], leflunomide [LEF]) will be allowed but are not required.

There will be a screening phase of approximately 6 weeks, a treatment phase of approximately 2 years that will include a double-blind placebo-controlled period from Week 0 to Week 24 and an active controlled treatment phase from Week 24 to Week 100, and a safety follow-up at Week 112 (approximately 12 weeks after the last intended dose at Week 100 per protocol).

An overview of the study design is provided in Figure 1.

medications up to the maximum allowed dose, as selected by the investigator.

At Week 0, participants who satisfy all inclusion and exclusion criteria will be randomly assigned to 1 of the following 3 treatment groups in a 1:1:1 ratio using permuted block randomization stratified by baseline non-biologic DMARD use (yes/no).

- Group I (n=150), guselkumab 100 mg SC every 8 weeks (q8w): Participants will receive SC guselkumab 100 mg at Weeks 0, 4 then q8 at Weeks 12, 20, 28, 36, 44, 52, 60, 68, 76, 84, 92, and 100. Participants will receive placebo SC at Weeks 8, 16, 24, 32, 40, 48, 56, 64, 72, 80, 88, and 96 to maintain the blind.
- Group II (n = 150), guselkumab 100 mg SC every 4 weeks (q4w): Participants will receive SC guselkumab 100 mg at Weeks 0, 4, then q4 at Weeks 8, 12, 16, 20, 24, 28, 32, 36, 40, 44 48, 52, 56, 60, 64, 68, 72, 76, 80, 84, 88, 92, 96, and 100.
- Group III (n=150), placebo and placebo cross-over: Participants will receive SC placebo at Weeks 0, 4, 8, 12, 16 and 20, and will cross over at Week 24 to receive SC guselkumab

3

[†] The first DBL will occur when all randomized participants have either completed the Week 24 assessments or terminated study participation prior to the Week 24 visit.

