5.3.3.2. Multiplicity Adjustment for Testing Procedures

This study has 1 primary endpoint (proportion of participants who achieved an ACR 20 response at Week 24) and 10 major secondary endpoints. With 11 endpoints and 2 treatment comparisons for each of these endpoints, there are a total of 22 hypotheses to be tested. These hypotheses are explicitly listed in Section 6.11.

The overall Type I error of the 22 hypotheses will be controlled at a significant level of ≤ 0.05 . The testing procedure tests the primary and selected major secondary endpoints, for the two regimens of guselkumab vs placebo, in a fixed sequence and each endpoint is tested at the two-sided 0.05 level of significance. The fixed sequence testing method tests an endpoint only if the null hypotheses of no difference between the gulsekumab regimen and placebo were rejected at the 0.05 level for all the endpoints above it in the sequence. This is shown visually in Figure 2 below.

Multiplicity Control Figure 2: Primary Endpoint ACR20 response at Week 24 (q4w vs placebo) If p≤0.05 ACR20 response at Week 24 (q8w vs placebo) If p≤0.05 Major Secondary Endpoints IGA response at Week 24 (q4w vs placebo) If p≤0.05 IGA response at Week 24 (q8w vs placebo) If p≤0.05 PASI 90 response at Week 24 (q4w vs placebo) If p≤0.05 PASI 90 response at Week 24 (q8w vs placebo) If p≤0.05 Change from baseline to Week 24 in HAQ-DI (q4w vs placebo) If p≤0.05 Change from baseline to Week 24 in HAQ-DI (q8w vs placebo) If p≤0.05 Change from baseline to Week 24 in SF-36 Physical Component Score (q4w vs placebo) If p≤0.05 Change from baseline to Week 24 in SF-36 Physical Component Score (q8w vs placebo) If p≤0.05 Change from baseline to Week 24 in FACIT-F (q4w vs placebo) If p≤0.05 Change from baseline to Week 24 in FACIT-F (q8w vs placebo) If p≤0.05 Achieving MDA at Week 24 (q4w vs placebo) If p≤0.05 Achieving MDA at Week 24 (q8w vs placebo)

For the weakly controlled hypothesis tests (see Section 3.2), p-values are not strictly controlled. However, as its test depends on the positive result of its correlated strongly controlled hypothesis test, there are some levels of control even though the level of control is not quantifiable. Although

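### SAP Table 4 gives single-test power for the multiplicity-controlled secondary endpoints; under the Figure 2 sequence the chance of claiming MDA on q4w is about 80–84%, not 99%

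*SAP*

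**What the plan says.** SAP 3.2 introduces Table 4 with "Table 4 provides the statistical power for major secondary with 150 participants per treatment group" and sums it up as "The study power ranges approximately from 44% to 99" percent. The power column is headed with n=150 and p=0.05. The rows stand under two labels: multiplicity controlled (IGA response, PASI 90, HAQ-DI, SF-36 PCS, FACIT-F, MDA) and weakly controlled (the ACR endpoints). The MDA rows on PSA3001 data read "MDA PSA3001 Q8 11.1% 22.8% 11.7% 78" percent and "PSA3001 Q4 11.1% 30.5% 19.4% 99" percent.

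SAP 5.3.3.2 sets the procedure: "each endpoint is tested at the two-sided 0.05 level of significance", and "The fixed sequence testing method tests an endpoint only if the null hypotheses of no difference between the gulsekumab regimen and placebo were rejected" at 0.05 for everything above it. Figure 2 draws one chain for both doses, q4w then q8w within each endpoint. Near its end it reads "Change from baseline to Week 24 in FACIT-F (q8w vs placebo) If p≤0.05 Achieving MDA at Week 24 (q4w vs placebo". Counted from ACR 20 at Week 24, there are 14 tests (H1 to H14 in SAP Appendix 10). MDA on q4w is 13th and MDA on q8w is 14th. The weakly controlled endpoints lie outside the chain.

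**The concern.** A reader who sees 99% under a multiplicity-controlled label, in a table summed up as study power, will take it as the chance that the plan lets q4w be declared superior on MDA. It is not. A test late in a fixed sequence cannot be claimed more often than any gate before it is passed. Because the doses alternate, a miss on q8w also stops q4w: if HAQ-DI, SF-36 PCS or FACIT-F fails on q8w, MDA on q4w is never formally tested, however strong its data. What is at stake is a realistic expectation of which secondary claims the trial can support, not the validity of those claims.

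**Working it through.** **Inputs.** n=150 per arm and two-sided 0.05 (SAP 3.2 and 5.3.3.2); randomisation "to 1 of the following 3 treatment groups in a 1:1:1 ratio using permuted block randomization" (SAP 1.2); rates, differences and SDs from Tables 3 and 4, using the PSA3001 rows and, for FACIT-F, PSA3002.

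**1. Reproduce the single-test figures.** For proportions, power = Φ[(d − 1.96·SE₀)/SE₁], with SE₀ pooled and SE₁ unpooled. For means, power = Φ[d/(SD·√(2/150)) − 1.96].

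MDA q4w: d = 0.194, SE₀ = √(2 × 0.208 × 0.792/150) = 0.0469, SE₁ = √((0.111 × 0.889 + 0.305 × 0.695)/150) = 0.0455. Power = Φ[(0.194 − 0.0919)/0.0455] = Φ(2.24) = 98.8%. The printed 99% is right as one test.

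| Test | Printed | Recomputed |
|---|---|---|
| HAQ-DI q4w (0.33/0.56) | >99% | 99.9% |
| HAQ-DI q8w (0.25/0.56) | 97% | 97.2% |
| SF-36 PCS q8w (4.14/7.72) | >99% | 99.6% |
| FACIT-F q4w (3.55/9.87) | 93% | 87.6% |
| FACIT-F q8w (3.99/9.87) | 87% | 93.8% |
| MDA q4w | 99% | 98.8% |
| MDA q8w | 78% | 77.3% |

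The ACR 20, IGA, PASI 90 and SF-36 PCS q4w tests all exceed 99.9%. The two FACIT-F cells look exchanged. Both precede MDA, so this hardly affects what follows.

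**2. A cap from the printed cells alone.** MDA on q4w needs both FACIT-F tests to succeed. Whatever the correlations, its chance cannot exceed the smallest gate, which is 87% as printed and 87.6% recomputed.

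**3. Correlation-free bounds.** The upper bound is the smallest single-test power, 87.6%. The lower bound is 1 minus the sum of the failure probabilities of tests 1 to 13. The main terms are 0.0283 (HAQ-DI q8w), 0.0036 (SF-36 PCS q8w), 0.1241 and 0.0617 (FACIT-F), and 0.0124 (MDA q4w); the rest add 0.0012. 1 − 0.2313 = 76.9%. For MDA on q8w the bounds are 54.2% to 77.3%.

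**4. Product of powers.** Recomputed powers multiply to 78.5% for MDA q4w and 60.7% for MDA q8w. The printed powers, with >99% taken as 1, give 0.97 × 0.93 × 0.87 × 0.99 = 77.7% for MDA q4w.

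**5. Simulation with correlation.** The 14 z-statistics were drawn as multivariate normal (500,000 draws), each with mean 1.96 + Φ⁻¹(its single-test power). Two contrasts that share an equal-sized placebo arm have correlation 0.5. The documents give no correlation between endpoints, so it was varied.

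| Between-endpoint correlation (assumed) | FACIT-F q8w | MDA q4w | MDA q8w |
|---|---|---|---|
| 0 | 81.3% | 80.3% | 62.6% |
| 0.2 | 81.7% | 80.9% | 64.3% |
| 0.5 | 82.3% | 81.9% | 67.2% |
| 0.7 | 83.0% | 82.8% | 69.1% |
| 0.9 | 83.8% | 83.8% | 71.0% |

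**6. Skin subset.** IGA and PASI 90 use a baseline subset whose size is not given. At an assumed 50% to 67% of 150 per arm, each skin test stays above 99.9% and the product for MDA q4w stays at 78.5%.

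**The case against.** The best defence is that Table 4 does not claim to be anything else. Its column heading names one n and one p, 99% is correct on that reading, and marginal power for secondary endpoints is often reported. The multiplicity label can be read as naming the family an endpoint belongs to. No decision rests on these cells: the sample size was set on ACR 20 at Week 24 (SAP 3), and the study is positive on H1 alone (SAP 2). All of this stands. It makes the point one of missing labelling and a missing column, not of a miscalculated cell.

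The inputs may also be conservative. Table 4 uses the largest arm SD, while the planned ANCOVA adjusts for baseline score. If the effective SD were 10% smaller (an assumption), FACIT-F would be about 93% and 97%, and HAQ-DI q8w 99%. The product for MDA q4w would then be about 0.93 × 0.97 × 0.99 × 0.988 = 88%, still well short of 99%.

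Three stronger readings are tempting but not supported:

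- A reader might infer that the trial is underpowered or that its error control fails. H1 stands first in the chain, and a fixed sequence at 0.05 is not in question here.
- A reader might put the PSA3003 rows in for q8w and report a larger loss. Most of that extra loss comes from one separately wrong cell: HAQ-DI 0.169/0.52 is printed as >99% and computes to 80.4%. The mixture also gives one shared placebo arm two MDA rates, 11.1% and 3.1%.
- A reader might say that FACIT-F on q4w is presented as nearly certain. It is printed at 93%.

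**Conclusion.** The point holds as one of reporting. Table 4's figures for the controlled endpoints are stand-alone power, and the plan's own procedure delivers less for the late ones. On PSA3001/PSA3002 inputs, MDA on q4w has about an 80–84% chance of being claimed, against 99% stated. MDA on q8w has about 63–71%, against 78% stated. These ranges assume a correlation of 0 to 0.9 between endpoints and 0.5 between doses. Without any correlation assumption, MDA on q4w lies between 77% and 88%, given Table 4's effect sizes and SDs. Nearly all the loss comes from the two FACIT-F tests and HAQ-DI on q8w.

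**What to change.** First correct the two separate cell problems: the apparently exchanged PSA3002 FACIT-F powers and the PSA3003 HAQ-DI power. Then:

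- Label the present column *stand-alone test*.
- Add a column of cumulative power for H1 to H14 in Figure 2 order, by simulation, with the assumed correlation range stated.
- Keep the 44% to 99% range, but say that it is stand-alone power across all ten major secondary endpoints. The 44% belongs to ACR 70 at Week 24 on q8w, which is weakly controlled and outside Figure 2, so sequence figures cannot replace it. Give the sequence-power range separately for the controlled endpoints.

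The cost is SAP wording and a short simulation. Some stated power figures become less favourable. Design, alpha and conduct do not change.

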4. STUDY DESIGN

4.1. Overall Design

This is a Phase 3b, multicenter, randomized, double-blind, placebo-controlled interventional study in participants with active PsA who had an IR and/or intolerance to one prior anti-TNF.

A target of 450 participants will be randomly assigned in this study with 150 participants planned per intervention group: Guselkumab q8w (n=150), guselkumab q4w (n=150), or placebo (n=150). Participants impacted by major disruptions may be replaced. Stable doses of concomitant NSAIDs, oral corticosteroids (\leq 10 mg/day prednisone equivalent), selected non-biologic DMARDs (MTX, SSZ, HCQ, LEF) will be allowed but are not required.

There will be a screening phase of up to 6 weeks, a treatment phase of approximately 2 years that will include a double-blind placebo-controlled period from Week 0 to Week 24 and an active-controlled treatment phase from Week 24 to Week 100, and a safety follow-up at Week 112 (approximately 12 weeks after the last intended dose at Week 100 per protocol).

At Week 0, participants who satisfy all inclusion and exclusion criteria will be randomly assigned to 1 of the following 3 treatment groups in a 1:1:1 ratio using permuted block randomization stratified by baseline non-biologic DMARD use (yes/no).

- Group I (n=150), guselkumab 100 mg SC every 8 weeks (q8w): Participants will receive guselkumab 100 mg SC at Weeks 0, 4, then q8w at Weeks 12, 20, 28, 36, 44, 52, 60, 68, 76, 84, 92, and 100. Participants will receive placebo SC at Weeks 8, 16, 24, 32, 40, 48, 56, 64, 72, 80, 88, and 96 to maintain the blind.
- **Group II (n=150), guselkumab 100 mg SC every 4 weeks (q4w):** Participants will receive guselkumab 100 mg SC at Weeks 0, 4, then q4w at Weeks 8, 12, 16, 20, 24, 28, 32, 36, 40, 44, 48, 52, 56, 60, 64, 68, 72, 76, 80, 84, 88, 92, 96, and 100.
- Group III (n=150), placebo and placebo crossover to guselkumab 100 mg SC q4w: Participants will receive placebo SC at Weeks 0, 4, 8, 12, 16 and 20, and will cross over at Week 24 to receive guselkumab 100 mg SC at Weeks 24, 28, then q4w at Weeks 32, 36, 40, 44, 48, 52, 56, 60, 64, 68, 72, 76, 80, 84, 88, 92, 96, and 100.

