5.3.3. Analysis Specifications

5.3.3.1. Level of Significance

In general, statistical testing will be performed using 2-sided tests. The overall Type I error will be controlled among the primary and major secondary endpoints at 5%.

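### SAP Table 4 prints >99% power for HAQ-DI (PSA3003, q8w) where its own inputs give 80%, at a step that gates six later tests; the two PSA3002 FACIT-F powers do not match their differences and look swapped

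*SAP*

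**What the plan says.** SAP Section 3.2 introduces the table with "Table 4 provides the statistical power for major secondary with 150 participants per treatment group". The rows at issue, each read as placebo mean, guselkumab mean, SD, difference and power in percent, are:

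- HAQ-DI, PSA3003, q8w: "0.009 -0.178 0.52 0.169 >99" (the minus sign of the placebo mean falls just before the quoted run)
- FACIT-F, PSA3002, q8w: "3.56 7.55 9.87 3.99 87"
- FACIT-F, PSA3002, q4w: "3.56 7.11 9.87 3.55 93"

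A footnote to Table 4 says the SD is the largest among the treatment groups.

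SAP Section 5.3.3.2 and Figure 2 put 14 hypotheses in one fixed sequence, in which "each endpoint is tested at the two-sided 0.05 level of significance" and a hypothesis is tested only if all those above it were rejected. The eighth is "Change from baseline to Week 24 in HAQ-DI (q8w vs placebo"). After it come SF-36 PCS, FACIT-F and MDA, each for q4w and then q8w.

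**The concern.** The table contradicts itself before any calculation.

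- **HAQ-DI.** The PSA3001 q8w row has a standardised difference of 0.25/0.56 = 0.446 and is given 97%. The PSA3003 q8w row has a smaller one, 0.169/0.52 = 0.325, and is given more than 99%. At equal group size and alpha that cannot be.
- **FACIT-F, PSA3002.** Both rows have SD 9.87 and 150 per group, yet the larger difference carries the lower power.

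The HAQ-DI cell matters most because of its place in the sequence. If HAQ-DI q8w misses 0.05, six hypotheses (H9 to H14) cannot be formally tested, including SF-36 PCS for q4w, which Table 4 gives more than 99% power on its own.

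PSA3003 is also the planning source closest to this trial's population. It enrolled participants with inadequate response or intolerance to up to two anti-TNFs. About 30% of PSA3001 participants were anti-TNF-experienced, 44 of them inadequate responders (Protocol Section 4.2), and PSA3002 was biologic-naïve (Protocol Section 2.2.1.1.1). A reader who uses the PSA3003 rows to judge the chain would take one of its weaker links for one of its strongest.

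**Working it through.** **Inputs.** 150 per group (SAP Section 3.2). Allocation is 1:1:1 (Protocol Section 4.1: "randomly assigned to 1 of the following 3 treatment groups in a 1:1:1 ratio"), so each comparison with placebo is 150 against 150. Alpha is 0.05, two-sided (SAP Section 5.3.3.1: "In general, statistical testing will be performed using 2-sided tests"). Differences and SDs are as printed in Table 4.

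**Formula.** Noncentrality = (difference/SD) × √(150/2) = (difference/SD) × 8.660. Normal-approximation power ≈ Φ(noncentrality − 1.960). The t column uses the noncentral t distribution with 298 degrees of freedom.

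**Undisputed continuous rows, to establish the method**

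| Row | Difference/SD | Noncentrality | Power, z | Power, t | Printed |
|---|---|---|---|---|---|
| HAQ-DI PSA3001 q8w | 0.25/0.56 = 0.446 | 3.87 | 97.2% | 97.1% | 97% |
| HAQ-DI PSA3001 q4w | 0.33/0.56 = 0.589 | 5.10 | 99.9% | 99.9% | >99% |
| SF-36 PCS PSA3001 q8w | 4.14/7.72 = 0.536 | 4.64 | 99.6% | 99.6% | >99% |
| SF-36 PCS PSA3001 q4w | 4.91/7.72 = 0.636 | 5.51 | 99.98% | 99.98% | >99% |
| SF-36 PCS PSA3003 q8w | 3.901/6.61 = 0.590 | 5.11 | 99.9% | 99.9% | >99% |
| FACIT-F PSA3003 q8w | 3.557/8.67 = 0.410 | 3.55 | 94.4% | 94.3% | 94% |

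Binary rows reproduce within 2 points under a two-proportion test. MDA gives 77.3%, 98.8% and 94.8% against 78%, 99% and 95% printed. ACR 70 gives 44.2%, 95.4% and 82.9% against 44%, 96% and 84%.

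**Disputed rows**

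| Row | Difference/SD | Noncentrality | Power, z | Power, t | Printed |
|---|---|---|---|---|---|
| HAQ-DI PSA3003 q8w | 0.169/0.52 = 0.325 | 2.81 | 80.4% | 80.1% | >99% |
| FACIT-F PSA3002 q8w | 3.99/9.87 = 0.404 | 3.50 | 93.8% | 93.7% | 87% |
| FACIT-F PSA3002 q4w | 3.55/9.87 = 0.360 | 3.12 | 87.6% | 87.4% | 93% |

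**What >99% would take for HAQ-DI.** With z-values 1.960 and 2.326, n per group = 2 × (1.960 + 2.326)² × (0.52/0.169)² ≈ 348 (349 by the t calculation). Alternatively, at 150 per group, it would take an SD of about 0.34 or a difference of about 0.257.

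**Other readings tried for the HAQ-DI row**

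- One-sided test: 87.9%.
- Both guselkumab groups pooled, 300 against 150: 90.0%.
- 300 per group: 97.8%.
- The guselkumab mean change of 0.178 used as the difference: 84.2%.
- ANCOVA with an assumed baseline correlation of 0.3 or 0.5: 83.9% or 90.1%. A correlation of about 0.75 would be needed for 99%.

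None reaches 99%. One-sided testing does not explain the FACIT-F pair either. It gives 92.9% for q4w, close to the printed 93%, but 96.8% for q8w against the printed 87%.

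**Consequence in the sequence.** The six later tests are reached only if HAQ-DI q8w is significant, so the probability of reaching them cannot exceed its power: about 80% under PSA3003 inputs. Every other PSA3003 row in the controlled family recomputes to at least 94%. SAP Section 3.1 considers 80% and 70% of the planned effect for ACR 20. Applied here for illustration, differences of 0.135 and 0.118 give 61% and 50%.

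**The case against.** The arithmetic is not in dispute. The case on the other side concerns its weight and the remedy.

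- **Nothing in the design depends on Table 4.** The sample size was set on ACR 20, whose power stays above 90% even at 70% of the PSA3003 effect. Test order, alpha and analyses do not use the table, and the study is declared positive on H1 alone. This stands and limits the weight of the point.
- **Lower powers are printed openly.** The same controlled block shows 78% for MDA q8w under PSA3001. True, but MDA q8w is the last step and gates nothing, whereas HAQ-DI q8w gates six tests.
- **The chance of passing all 14 steps is well below 1 anyway.** Under PSA3001/PSA3002 inputs as printed, with independence and the >99% entries taken as 1, it is 0.97 × 0.87 × 0.93 × 0.78 × 0.99 ≈ 0.61. For that reason this point rests only on the 80% cap, which needs no correlations or skin-subset sizes. Exchanging the two FACIT-F powers does not change that product.
- **The planned ANCOVA adjusts for baseline and may do better than 80%.** Correct. The figure is the power at the table's inputs, not a forecast. At assumed correlations of 0.3 to 0.5 it is 84% to 90%, still well short of the printed value.
- **An input, not the power, may be wrong.** The HAQ-DI SD could be mis-entered, or the FACIT-F means could be transposed rather than the powers. The documents cannot settle this, so the fix starts with a source check.
- **PSA3003 may be the more refractory population.** It allowed up to two prior anti-TNFs and this trial allows one. That is a fair caution, but the SAP names PSA3003 as a planning source, so its row should be right.

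**Conclusion.** The concern holds. At Table 4's own inputs, HAQ-DI q8w under PSA3003 has about 80% power, roughly 19 points below the printed figure. The two PSA3002 FACIT-F powers are inconsistent with their rows by about 6 to 7 points, in a pattern that fits a swap. The result assumes 150 evaluable per group, a two-sided 0.05 test, the printed SDs, no dropout (none is stated) and no gain from baseline adjustment.

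Under PSA3003, formal testing of SF-36 PCS, FACIT-F and MDA for both doses therefore rests on a step with about 80% power. Under PSA3001 the same step has 97%, so the misstatement is confined to the PSA3003 scenario. Practical weight is moderate: type I error, sample size and ACR 20 power are untouched, but the stated strength of the confirmatory chain is wrong.

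**What to change.** Check the means and SDs of the three rows against the source study reports and recompute. If the inputs stand, change HAQ-DI PSA3003 q8w to 80%, FACIT-F PSA3002 q8w to 94% and FACIT-F PSA3002 q4w to 87%. If an input is wrong, correct it and restate that row's power.

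Optionally, add one sentence to SAP Section 3.2 or 5.3.3.2 saying that under PSA3003 assumptions the probability of proceeding past HAQ-DI q8w is at most about 80%.

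The cost is a correction to one SAP table. The stated HAQ-DI power becomes less favourable. Sample size, test order, analysis and participant numbers do not change.
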